4 STUDY DRUG

Study drug includes both Investigational [Medicinal] Product (IP/IMP) and Non-investigational [Medicinal] Product (Non-IP/Non-IMP) and can consist of the following:

- All products, active or placebo, being tested or used as a comparator in a clinical trial
- Study required premedication
- Other drugs administered as part of the study that are critical to claims of efficacy (eg, background therapy, rescue medications)
- Diagnostic agents: (such as glucose for glucose challenge) given as part of the protocol requirements must also be included in the dosing data collection

The study treatments include BMS-663513 and BMS-936558. Table 4-1 below indicates the dose level to be used for each panel.

Table 4-1: Treatment Administration

Cohort	Urelumab (BMS-663513)	Subjects Enrolled Prior to Revised Protocol 02	Subjects Enrolled After Revised Protocol 02
		Nivolumab (BMS-936558)	Nivolumab (BMS-936558)
1	3 mg IV every 4 weeks	3 mg/kg IV every 2 weeks	240 mg IV every 2 weeks
2	8 mg IV every 4 weeks	3 mg/kg IV every 2 weeks	240 mg IV every 2 weeks
A ^a	8 mg IV every 8 weeks	3 mg/kg IV every 2 weeks	240 mg IV every 2 weeks
B ^a	8 mg IV every 8 weeks	1 mg/kg IV every 2 weeks	80 mg IV every 2 weeks
C	3 mg IV every 4 weeks	1 mg/kg IV every 2 weeks	80 mg IV every 2 weeks
D ^a	3 mg IV every 8 weeks	3 mg/kg IV every 2 weeks	240 mg IV every 2 weeks

^a Dosing regimen not applicable following Revised Protocol 03 (Dated 31-Aug-2015)

Product description and storage information is described in [Table 4-2](#).

Expansion cohorts will be treated at the highest tested dose or a different dose level as selected by the sponsor.

For treatment visits where both BMS-663513 and BMS-936558 are administered, BMS-936558 will be administered first followed by BMS-663513 at least 30 minutes after completion of the BMS-936558 infusion. Detailed administration instructions will be provided separately via site training materials.

Table 4-2: **Study Drugs for CA186107**

Product Description Class and Dosage Form	Potency	IP/Non-IMP	Blinded or Open Label	Packaging/Appearance	Storage Conditions (per label)
Urelumab (BMS-663513-01) Injection (for IV Infusion)	5 mg/ mL	IP	Open Label	3 mL fill in a 5 mL vial/ 1 vial/ carton A clear colorless to pale yellow solution which may contain particulates	Store refrigerated, 2° - 8° C, (36° - 46° F) Protect from Light, Protect from Freezing.
Nivolumab (BMS-936558-01) Injection, 100 mg/vial (10 mg/mL)	10 mg/mL	IP	Open Label	10 mL vial Box Clear to opalescent, colorless to pale yellow liquid. May contain light (few) particulates	Store 2-8 Degrees C (36-46 Degrees F); Protect from Light; Protect from Freezing Protect from Shaking.

4.1 Investigational Product

An investigational product, also known as investigational medicinal product in some regions, is defined as follows:

A pharmaceutical form of an active substance or placebo being tested or used as a reference in a clinical study, including products already with a marketing authorization but used or assembled (formulated or packaged) in a way different from the authorized form, or used for an unauthorized indication, or when used to gain further information about the authorized form.

The investigational product should be stored in a secure area according to local regulations. It is the responsibility of the investigator to ensure that investigational product is only dispensed to study subjects. The investigational product must be dispensed only from official study sites by authorized personnel according to local regulations.

In this protocol, investigational product(s) is/are: urelumab (BMS-663513) and nivolumab (BMS-936558).

4.2 Noninvestigational Product

Other medications used as support or escape medication for preventative, diagnostic, or therapeutic reasons, as components of the standard of care for a given diagnosis, may be considered as noninvestigational products.

4.3 Storage and Dispensing

The product storage manager should ensure that the study drug is stored in accordance with the environmental conditions (temperature, light, and humidity) as determined by BMS. If concerns regarding the quality or appearance of the study drug arise, do not dispense the study drug and contact BMS immediately.

Study drug not supplied by BMS will be stored in accordance with the package insert.

Investigational product documentation (whether supplied by BMS or not) must be maintained that includes all processes required to ensure drug is accurately administered. This includes documentation of drug storage, administration and, as applicable, storage temperatures, reconstitution, and use of required processes (eg, required diluents, administration sets).

Infusion-related supplies (eg, IV bags, in-line filters, 0.9% NaCl solution) will not be supplied by the sponsor and should be purchased locally if permitted by local regulations.

For non-investigational product, if marketed product is utilized, it should be stored in accordance with the package insert, summary of product characteristics (SmPC), or similar.

Please refer to the current version of the Investigator Brochure/pharmacy reference sheets for complete storage, handling, and preparation information for BMS-663513 (urelumab) and BMS-936558 (nivolumab).

4.3.1 *BMS-663513 (urelumab)*

The product storage manager should ensure that the study drug is stored in accordance with the environmental conditions (temperature, light, and humidity) as determined by BMS. If concerns

regarding the quality or appearance of the study drug arise, the study drug should not be dispensed and contact BMS immediately.

Investigational product documentation must be maintained that includes all processes required to ensure drug is accurately administered. This includes documentation of drug storage, administration and, as applicable, storage temperatures, reconstitution, and use of required processes (eg, required diluents, administration sets).

As with all injectable drugs, care should be taken when handling and preparing urelumab. Whenever possible, urelumab should be prepared in a laminar flow hood or safety cabinet using standard procedures for the safe handling of intravenous agents applying aseptic techniques. Gloves are required.

If urelumab solution comes in contact with the skin or mucosa, immediately and thoroughly wash with soap and water.

Urelumab injection is an isotonic solution that may be diluted to concentrations between 0.05 mg/mL and 1 mg/mL using sterile disposable syringes prior to administration by IV infusion. Solutions of urelumab injection may foam; therefore, shaking and excessive agitation of vials should be avoided. Gentle swirling and inversion of the vials is recommended prior to dilution. The urelumab drug product solution may be diluted with 0.9% sodium chloride injection normal saline (NS), United States Pharmacopeia, in non-PVC/non-DEHP IV bags. The product must be infused using a volumetric pump at the protocol specific dose(s) and rate(s) through a sterile, non-pyrogenic, non-PVC/non-DEHP, IV infusion set containing a 0.2 μ m polyethersulfone in-line filter. It is not to be administered as IV push or bolus injection. Care must be taken to assure sterility of the prepared solutions, since the drug product does not contain any antimicrobial preservatives or bacteriostatic agents. The diluted solutions may be stored for up to 4 hours at ambient room temperature/room light, or for up to 24 hours in a refrigerator 2°C to 8°C (36°F to 46°F), but must be infused within each timeframe, respectively.

The infusion rates should be maintained at either 1.0 mL/min for the 60 minute infusion or at 0.5 mL/min if the rate has been reduced by half due to an infusion reaction. A minimum of 10 mL normal saline flush should be given at the end of the infusion. For convenience the infusion times and volumes for the various cohorts are listed below and should be used accordingly:

Dose escalation and dose expansion cohorts 8 mg or 3 mg dose per subject

- Infusion volume: 60 mL
- Infusion time: 60 min (1 mL/min)

Sample calculation for required volume of urelumab based on dose:

- Subject at 8 mg dose
- Total dose: 8 mg
- Volume urelumab: $8 \text{ mg} / (5 \text{ mg/mL}) = 1.6 \text{ mL}$

For non-investigational product, if marketed product is utilized, it should be stored in accordance with the package insert, summary of product characteristics (SmPC), or similar.

4.3.2 BMS-936558 (*nivolumab*)

Nivolumab vials must be stored at a temperature of 2°C to 8°C and should be protected from light and freezing. If stored in a glass front refrigerator, vials should be stored in the carton. Recommended safety measures for preparation and handling of nivolumab include laboratory coats and gloves.

For details on drug preparation, storage, handling and dispensing of nivolumab, please refer to the BMS-936558 (nivolumab) Investigator Brochure and/or pharmacy reference sheets.

Nivolumab is to be administered as a 60-minute IV infusion. When both study drugs are to be administered on the same day, separate infusion bags and filters must be used for each infusion. Nivolumab is to be administered first followed by urelumab at least 30 minutes after completion of the nivolumab infusion. The nivolumab infusion must be promptly followed by a saline flush to clear the line of nivolumab before starting the urelumab infusion.

Detailed administration instructions will be provided separately via site training materials.

4.4 Method of Assigning Subject Identification

CA186107 is an open label study. Subjects will undergo screening evaluations to determine eligibility within 28 days prior to dosing. Enrolled subjects, including those not dosed, will be assigned sequential subject numbers starting with 00001, eg, 00001, 00002, 00003, ...00010. Those enrolled subjects meeting inclusion and exclusion criteria will be eligible to be treated and increasing sequentially with each additional enrolled subject. The subject number will be assigned by the Sponsor via Interactive Voice Response System (IVRS) once the subject signs the informed consent form. Each subject will then be identified by a distinct patient identification number (PID) which is comprised of the site number and the subject number. For example, the first subject screened (ie, enrolled) at site number 1, will have a PID of 0001 00001. The Investigator or designee will register the subject following the enrollment procedures established by BMS. The following information is required for registration:

- Date of birth
- Gender
- Date of Informed Consent
- Diagnosis (Expansion Phase only)
- Tumor Type (Expansion Phase only)

Enrolled subjects meeting all eligibility criteria will be assigned to a dose cohort.

Specific instructions for using IVRS will be provided to the investigational sites in a separate document.

4.5 Selection and Timing of Dose for Each Subject

Each subject will be assigned to a specific dose level as listed in [Table 4-1](#) in sequential order during dose escalation. Subjects in cohort expansion will be treated at the MTD, the HAD, or at an alternate dose, if recommended by the investigators and the sponsor.

Dosing calculations for nivolumab should be based on the body weight assessed at Day 1 per [Table 5.1-1](#). If the subject's weight on the day of dosing differs by > 10% from the weight used to calculate the dose, the dose must be re-calculated. All doses should be rounded to the nearest milligram. There will be no dose escalations or reductions of nivolumab allowed once assigned. Subjects may be dosed no less than 12 days from the previous dose. There are no premedications recommended for nivolumab on the first cycle. If an acute infusion reaction is noted, the subjects should be managed according to [Section 4.5.9](#).

Following implementation of revised protocol 02, nivolumab will be administered as flat dosing at the doses listed in [Table 4-1](#).

Urelumab will be administered as flat dosing at the doses listed in [Table 4-1](#).

4.5.1 Antiemetic Premedications

Antiemetic premedications should not be routinely administered prior to dosing of study drug. See [Section 4.5.9](#) for subsequent premedication recommendations following a nivolumab-related infusion reaction.

4.5.2 Dose Limiting Toxicities

Adverse events will be graded according to the National Cancer Institute (NCI) Common Terminology Criteria for Adverse Events (CTCAE) Version 4.0 (v4.0).

Non-hematologic Dose-Limiting Toxicity (DLT):

A. Hepatic Non-Hematologic DLT

Any one of the following study drug-related events will be considered a hepatic DLT:

- Any \geq grade 3 elevation of AST, ALT or T bili
- Grade 2 AST or ALT with symptomatic liver inflammation (eg, right upper quadrant tenderness, jaundice, pruritus)
- AST or ALT $> 3 \times$ ULN and concurrent total bilirubin $> 2 \times$ ULN without initial findings of cholestasis (elevated serum alkaline phosphatase (ALP) (ie, findings consistent with Hy's law or FDA definition of potential drug-induced liver injury or pDILI)*

*[Note that this special category of DLT uses ULN rather than CTC Grade for definition]

NOTE: Subjects who experience a DLT that is considered related only to urelumab may be allowed to continue nivolumab monotherapy following resolution of the event. This will be determined on a case by case basis, after specific consultation and agreement between the investigator and BMS Medical Monitor in settings where benefit/risk may justify continued treatment with nivolumab

monotherapy (eg, subjects with asymptomatic, isolated grade 3 ALT and/or AST elevation that responds rapidly to short 2-3 weeks course of steroid therapy).

B. Non-Hepatic Non-Hematologic DLT

Any of the following events will be considered a Non-Hepatic Non-Hematologic DLT:

- Any Grade 2 drug-related uveitis or eye pain or blurred vision that does not respond to topical therapy and does not improve to Grade 1 severity within 2 weeks OR requires systemic treatment
- Grade 3 drug-related uveitis, pneumonitis, bronchospasm, neurologic toxicity, hypersensitivity reaction, or infusion reaction of any duration requires discontinuation
- Any Grade 3 or greater non-dermatologic, non-hepatic non-hematologic study drug-related toxicity will be considered a dose-limiting toxicity with the following specific EXCEPTIONS:
 - Grade 3 or grade 4 electrolyte abnormalities that are not complicated by associated clinical adverse experiences, last less than 48 hours and either resolve spontaneously or respond to conventional medical intervention
 - Grade 3 nausea, vomiting or diarrhea that lasts less than 48 hours, and either resolves spontaneously or responds to conventional medical intervention
 - Isolated Grade 3 elevation of amylase or lipase not associated with clinical or radiographic evidence of pancreatitis
 - Isolated Grade 3 fever not associated with hemodynamic compromise (eg, hypotension, clinical or laboratory evidence of impaired end-organ perfusion)

C. Dermatologic DLT

- Grade 3/4 rash if no improvement (ie, resolution to \leq Grade 1) after a 1-2 week infusion delay. Subjects who have not experienced a Grade 3 drug-related skin AE may resume treatment in the presence of Grade 2 skin toxicity

D. Hematologic DLT (study drug-related)

- Grade 4 neutropenia \geq 7 days in duration
- Grade 4 thrombocytopenia or Grade 3 thrombocytopenia with bleeding, or any requirement for platelet transfusion
- Grade \geq 3 febrile neutropenia for 72 hours
- Grade \geq 3 hemolysis (ie, requiring transfusion or medical intervention such as steroids)
- Grade 4 anemia not explained by underlying disease

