3.1.5 Dose Escalation

A 3+3+3 design will be used to assess the safety of urelumab given in combination with nivolumab. The cohorts for dose escalation are provided in [Table 3.1.5-1](#). The Dose Limiting Toxicity (DLT) observation period will last for 8 weeks following the first dose of study medication. The DLT evaluation period will be defined as 8 weeks after administration of the first combination dose of nivolumab and urelumab, and includes subjects who have had administration

of at least one dose of nivolumab monotherapy during this interval. This interval is based upon inclusion of the earliest times to onset of clinically significant adverse events attributed to study drug, and also allows for a substantial amount of time for unexpected toxicities related to the dosing regimen to emerge.

Approximately three subjects will be treated initially at each dose regimen. In order to assure a sufficient number of evaluable subjects in each cohort an additional subject may be added to a cohort (ie, enroll a fourth subject in a cohort of 3). For example, if 4 subjects are treated in the cohort, the decision to enroll additional patients or escalate will be made after the 3rd evaluable patient completes the DLT window. In this situation, if the decision is made to remain at the same dose level and the 4th patient is evaluable, he/she will be included as part of the 2nd cohort at that dose level.

Note: (i) Should this action be taken, cohort tolerability assessment and subsequent dose escalation, if indicated, will occur when the minimum number of evaluable subjects required to assess tolerability have completed the 8 week DLT period. (ii) If any additional subject experiences an event that would, per protocol, result in either cohort expansion or the halting of dose escalation, the escalation rules as defined below in [Table 3.1.5-2](#) will be followed.

Table 3.1.5-1: Dosages during Dose Escalation

Cohort	Total Subjects ^a	urelumab	nivolumab ^b
1	n = approximately 3-9	3 mg IV every 4 weeks	3 mg/kg or 240 mg IV every 2 weeks
2	n = approximately 3-9	8 mg IV every 4 weeks	3 mg/kg or 240 mg IV every 2 weeks
Total	n = approximately 6-18		

^a 3-9 subjects will be enrolled during dose escalation. Additional subjects may be added to each dose level for a total of up to 12 subjects per dose level

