^b Nivolumab 3 mg/kg will be administered for subjects enrolled prior to Revised Protocol 02. Nivolumab 240 mg flat dose administered for subjects enrolled after Revised Protocol 02.

After dose escalation to the next cohort, 3-9 additional subjects may be enrolled in any previously tolerated (as defined by the dose escalation decision rules in [Table 3.1.5-2](#)) dose level (original 3-9 subjects from dose escalation plus additional subjects required to have a total cohort size of 12). If the rate of DLTs exceeds 33% in a given treatment regimen, the findings will be discussed and further enrollment may be interrupted for that specific treatment regimen and tumor type.

If one of the planned dose cohorts is determined to exceed the MTD, and/or based on ongoing safety/tolerability experience through the dose escalation phase of the study, an alternate dose escalation schema as outlined in [Table 3.1.5-3](#) may be explored in consultation and agreement between the Sponsor and investigators.

Sentinel Subject: During dose escalation, the first subject treated at each dose level will receive C1D1 (eg, the first dose of study drugs) and will be observed for 3 weeks such that one combination dose followed by one nivolumab dose are administered before additional subjects in the cohort receive the first dose of study drug (ie, C1D1).

Dose Escalation Rules: Table outlines the decision rules for dose escalation based on the number of subjects and observed DLTs. No intra-subject dose escalation or reduction is allowed. Subjects who withdraw from the study during the DLT period for reasons other than a DLT may be replaced within the same dose level/regimen. Dose escalation will be based on the number of dose limiting toxicities (DLTs) experienced during the DLT observation period.

If dose escalation is terminated, then the dose or dosing regimen below that which invoked the stopping rule will be declared the MTD.

Table 3.1.5-2: Decision Rules During Dose Escalation

Number of Evaluable Subjects/ Cohort	3-4 ^a			6-8			9-12	
Total Number of Observed DLTs	0	1	2 or more	1	2	3 or more	2	3 or more
Decision Rule	Dose Escalate	Enroll additional subjects in cohort to reach at least 6 subjects	Dose exceeds MTD	Dose Escalate	Enroll additional subjects at in cohort to reach at least 9 subjects	Dose exceeds MTD	Dose Escalate	Dose exceeds MTD

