4.5.7 Guidelines for Permanent Discontinuation

Subjects will be required to permanently discontinue both study drugs for the following adverse events:

- A. Any drug related AE occurring at any time that meets DLT criteria as outlined in [Section 4.5.2](#) will require permanent discontinuation with the following **exceptions**:
 - a) grade 3 diarrhea, nausea, vomiting, or abdominal pain that returns to grade 1 or baseline within 3 days with medical intervention;
 - b) grade 3 pruritus or rash that returns to grade 1 or baseline within 7 days or baseline with medical intervention;
 - c) grade 4 electrolyte abnormalities that < 72 hours in duration;
 - d) grade 4 neutropenia \leq 7 days in duration;
 - e) grade 4 increase in amylase or lipase that is not associated with clinical or radiographic evidence of pancreatitis;
 - f) grade 4 lymphopenia < 5 days in duration.

NOTE: Subjects who experience a DLT that is considered related only to urelumab may be allowed to continue nivolumab monotherapy following resolution of the event. This will be determined on a case by case basis, after specific consultation and agreement between the investigator and BMS Medical Monitor in settings where benefit/risk may justify continued treatment with nivolumab monotherapy (eg, subjects with asymptomatic, isolated grade 3 ALT and/or AST elevation that responds rapidly to short 2-3 weeks course of steroid therapy).

Any dosing delay lasting > 6 weeks will be cause for permanent discontinuation with the following exceptions:

- Dosing delays to allow for prolonged steroid tapers to manage drug-related adverse events are allowed. Prior to re-initiating treatment in a subject with a dosing delay lasting > 6 weeks, the BMS Medical Monitor must be consulted. Tumor assessments should continue as per protocol even if dosing is delayed.

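### Protocol 4.5.2 leaves severe skin reactions other than persistent rash outside the DLT definition, and 4.5.7 A(b) excepts skin events that 4.5.2 C does not count

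*Protocol*

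**What the plan says.** The general rule in Protocol 4.5.2 B reads: "Any Grade 3 or greater non-dermatologic, non-hepatic non-hematologic study drug-related toxicity will be considered a dose-limiting toxicity", followed by listed exceptions. Hepatic and hematologic events, which it also excludes, get their own multi-item lists (A and D). Skin gets list C, which has a single DLT criterion: "Grade 3/4 rash if no improvement", improvement being defined as resolution to Grade 1 or less, assessed "after a 1-2 week infusion delay". The other sentence in C is about resuming treatment and adds no criterion.

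List B also names some reactions that could involve the skin: "Grade 3 drug-related uveitis, pneumonitis, bronchospasm, neurologic toxicity, hypersensitivity reaction, or infusion reaction of any duration requires discontinuation".

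Section 4.5.7 A requires permanent discontinuation of both drugs for drug-related events that meet the DLT criteria, with exceptions. Exception (b) is "grade 3 pruritus or rash that returns to grade 1 or baseline within 7 days or baseline with medical intervention".

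Section 3.1.5 gives the DLT definition its weight: "Dose escalation will be based on the number of dose limiting toxicities (DLTs) experienced during the DLT observation period", and "If dose escalation is terminated, then the dose or dosing regimen below that which invoked the stopping rule will be declared the MTD". The 33% review triggers in 3.1.5 and 3.1.6.1 use the same class of event.

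**The concern.** Skin is carved out of the general rule and only partly put back, so some severe drug-related skin reactions have no place in the DLT classification. If such an event occurred, the escalation table, the MTD declaration and the 33% trigger would treat the subject as free of DLT. The discontinuation requirement tied to DLT criteria would not apply either. Every omission works in the same direction, toward calling a regimen tolerated.

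Identifying DLTs and the MTD is a primary objective. Discontinuation for DLT-type events applies at any time on study, so the wording still matters for the roughly 50 PD-L1 negative melanoma subjects being added after escalation.

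**Working it through.** The plan states no figure that depends on this definition, so there is none to reproduce. The check is a reading of the passages against each other, followed by arithmetic on stated assumptions.

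**1. Classifying drug-related skin events under 4.5.2** (days counted from the start of the infusion delay, an assumption because the protocol does not say)

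| Event | General rule in B | Named reactions in B | List C | Literal result |
|---|---|---|---|---|
| Grade 3/4 rash, above Grade 1 after two weeks | excluded | no | met | DLT |
| Grade 3/4 rash, Grade 1 by day 10 | excluded | no | met at one week, not at two | two answers |
| Grade 3/4 rash, Grade 1 before day 7 | excluded | no | not met | not a DLT (possibly intended) |
| Grade 5 rash | excluded | no | grade not named | unclear |
| Grade 3-5 non-rash reaction, such as blistering | excluded | only if so classed | not rash | not a DLT unless so classed |
| Grade 3 pruritus alone | excluded | only if so classed | not rash | not a DLT unless so classed |

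The named item in B gives Grade 3 only. A higher-grade reaction classed as hypersensitivity would reach the general rule as a non-dermatologic event.

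**2. Comparison with 4.5.7 A(b).** The exceptions apply to events that already meet DLT criteria. Pruritus appears in 4.5.2 A only as a symptom that makes a Grade 2 transaminase elevation a hepatic DLT; by itself it is not listed. A rash that clears within 7 days cannot still be unresolved after a delay of at least one week. So (b) excepts events that 4.5.2 C does not count.

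**3. Effect on an escalation decision (Table 3.1.5-2).** With three evaluable subjects, 0 DLTs means escalate, 1 means enroll to at least 6, and 2 or more means the dose exceeds the MTD. If the only severe event among three subjects is one uncounted skin event, the decision changes from enrolling to at least 6 to escalating.

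**4. Illustration of size.** Let p be the per-subject DLT probability, with cohorts of exactly 3, 6 and 9. With b0 = (1−p)³ and b1 = 3p(1−p)²,

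P(escalate) = b0 + b1·b0 + b1²·b0 = b0(1 + b1 + b1²).

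In a cohort of 20, 6/20 = 30% does not exceed 33% and 7/20 = 35% does, so the trigger is met with probability P(X ≥ 7), X ~ Bin(20, p).

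Assume that 2%, 5% or 10% of subjects have an uncounted skin event as their only dose-limiting event, and that the rate with everything counted is 33%.

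- All counted, p = 0.33: 0.3008 × 1.6419 = 0.49
- 5% uncounted, p = 0.28: 0.3732 × 1.6251 = 0.61

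| Uncounted | p used | P(escalate) | P(at least 7 of 20) |
|---|---|---|---|
| 0 | 0.33 | 49% | 51% |
| 2% | 0.31 | 54% | 43% |
| 5% | 0.28 | 61% | 32% |
| 10% | 0.23 | 72% | 16% |

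At a low rate the effect is small. Take 6% counted (the treatment-related discontinuation rate in Protocol 1.5, a rough stand-in because discontinuations are not DLTs) plus 5% uncounted. P(escalate) is then 98% instead of 94%, and P(at least 7 of 20) is below 0.5% either way.

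The chance of at least one uncounted event in three subjects, 1 − (1−q)³, is 6%, 14% and 27% for q = 2%, 5% and 10%.

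**The case against.** The strongest reply is that this is a narrow wording gap with many backstops. Much of that stands.

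- **Other safeguards.** A reader might infer that DLT counts are the only safety input. They are not. Two Hy's law events independently place a dose above the MTD (1.5). Stage 2 needs sponsor review and investigator endorsement (3.1.6.1). Investigators must stop treatment when an adverse event makes continuing against the subject's interest (3.5). Resumption after an event with clinical risk is decided case by case (4.5.6). Drug-related events of Grade 2 or higher get expedited notification (6.7.2). Skin is a category of special interest in SAP 7.6.5. The 33% rule prompts discussion and possible interruption, not an automatic stop. None of these puts a skin event into the DLT count.
- **The 4.5.7 list.** It is tempting to read (b) as revealing a different intended skin rule, under which longer-lasting Grade 3 rash or all Grade 4 rash leads to discontinuation. The text does not support that, because an event must meet DLT criteria before the exceptions apply. The list has other redundant items: Grade 4 lymphopenia under 5 days is not a DLT in list D, and Grade 4 neutropenia of 7 days or less overlaps D only at exactly 7 days. The item shows inconsistency, no more.
- **Resolving rash.** Leaving out a Grade 3/4 rash that clears during the delay may be deliberate, so it is not called an error here. DLT counting and subject management also serve different purposes, so different durations in 4.5.2 and 4.5.7 are not wrong in themselves.
- **Expected frequency.** The rash (18.3%) and pruritus (11.7%) rates in 1.4.3 might be taken as evidence that severe skin events are common. They are not Grade 3+ rates, and they come from urelumab monotherapy across a wide dose range. In that section's every-3-week comparison, 189 subjects received 1 mg/kg or more and 44 received less, while 1.5 relates 8 mg to 0.1 mg/kg.

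The skin algorithm in Appendix 3 was not available for this check. Section 4.5.3 describes it as help with managing events, not as part of the DLT definition.

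**Conclusion.** The gap holds on the current text. Severe drug-related skin reactions other than rash enter the DLT count only if classed as hypersensitivity or infusion reactions. Grade 5 rash is not named, the one-to-two-week condition is ambiguous for rash clearing between days 7 and 14, and 4.5.7 A(b) does not fit 4.5.2 C. Nothing in the protocol or SAP text reviewed resolves this.

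The direction of any bias is clear; its size is not. The shifts in the illustration depend on assumed skin rates of 2-10% and an overall rate near 33%, and they nearly vanish at low rates. The documents do not show that any skin event was missed or that the dose chosen for expansion is wrong: 1.5 reports 138 treated patients with no treatment-related deaths, but gives no skin data by grade. This is a defect of definition that could misclassify individual subjects, and it is cheap to repair.

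**What to change.** Reconcile 4.5.2 B, 4.5.2 C and 4.5.7 A(b) so that:

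- every drug-related Grade 3-5 dermatologic event, rash or not, is explicitly a DLT or explicitly not one;
- the time condition for rash gives one answer for any resolution date;
- the discontinuation exceptions refer only to events that can be DLTs.

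The sponsor's clinicians set the grades and durations, and the two sections may keep different limits if that is intended and stated. When DLTs are reported, re-read the skin events already observed against the reconciled definition and note any whose classification changes.

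The cost is protocol wording and a limited review of existing adverse event records. The one downside is that the reported DLT rate may become slightly less favourable.
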